2. RATIONALE

Adrenal suppression effects of topical corticosteroids, especially super-high potency or Class I corticosteroids, are among the most important safety concerns for this group of products. This study is designed to determine the adrenal effects of the investigational lotion formulation of halobetasol propionate, 0.05% and characterize the steady-state

pharmacokinetics of the investigational lotion formulation in male and female subjects aged 12 to 16 years 11 months with stable plaque psoriasis.

3. OBJECTIVE

The objective of this study is to determine the adrenal suppression potential and the PK properties of an investigational lotion formulation of halobetasol propionate, 0.05% (HBP Lotion) applied twice daily in subjects aged 12 to 16 years 11 months with stable plaque psoriasis.

4. STUDY DESIGN

This is an open label, multicenter study of an investigational formulation of HBP Lotion, 0.05% in male and female subjects aged 12 to 16 years 11 months with stable plaque psoriasis. Approximately 25 subjects with stable plaque psoriasis on at least 10% of their BSA (excluding the face, scalp, groin, axillae and other intertriginous areas), who fulfill the inclusion/exclusion criteria will be enrolled at multiple study sites. All subjects will have a screening CST to assess their HPA axis response at Visit 1 (Screening Visit). Enrollment into the treatment phase of the study should be timed such that the screening CST will be performed a minimum of 20 days before Baseline Visit. At Visit 2 (Baseline), eligible subjects with normal adrenal function will be eligible to participate in the study.

Subjects will apply HBP Lotion, 0.05% to all psoriasis plaques identified at Visit 2 twice daily (approximately every 12 hours) for the assigned treatment period or until the investigator verifies the subject's psoriasis has cleared. The study is designed to determine the adrenal suppression potential and pharmacokinetic properties of the test article after the subject applies a maximum of approximately 50 grams per week for up to a two week treatment period. All subjects will have a CST to reassess their HPA axis response at EOS (or earlier if the investigator verifies the subject's psoriasis has cleared). In this study, an abnormal HPA axis response to 0.25 milligram dose of cosyntropin is defined as a post-CST serum total cortisol level of $\leq 18 \mu\text{g/dL}$.

5. STUDY POPULATION

5.1 Subject Eligibility

To be included in the study, subjects must meet the following inclusion and none of the exclusion criteria.

5.1.1 Inclusion Criteria

1. Subject is male or non-pregnant female
2. Subject has provided written informed assent and was accompanied by the parent or legal guardian at the time of assent/consent signing. The parent or legal guardian has provided informed consent for the subject.
3. Subject has a clinical diagnosis of stable plaque psoriasis involving a minimum of 10% BSA
4. Subject has an Investigator's Global Assessment (IGA) score of at least three (3 = moderate) at the Baseline Visit.
5. Subject is willing and able to apply the test article as directed, comply with study instructions and commit to all follow-up visits for the duration of the study.
6. Females must have a negative urine pregnancy test (UPT)⁵ at the Screening (Part B) and Baseline Visits and agree to use an effective form of birth control⁶ for the duration of the study.

5.1.2 Exclusion Criteria

1. Subject has spontaneously improving or rapidly deteriorating plaque psoriasis.
2. Subject has guttate, pustular, erythrodermic or other non-plaque forms of psoriasis.
3. Subject has a physical condition which, in the investigator's opinion, might impair evaluation of plaque psoriasis, adrenal axis function (e.g., Addison's Disease, Cushing's Syndrome) or which exposes the subject to an unacceptable risk by study participation.
4. Subject has used any phototherapy (including laser), photo-chemotherapy or systemic psoriasis therapy including methotrexate, retinoids, cyclosporine or biologics within 30 days prior to the initiation of treatment with the test article.
5. Subject has used systemic corticosteroids (including oral or intramuscular) or topical, inhaled or intranasal corticosteroids within 30 or 14 days, respectively, prior to Part B of the Screening Visit and/or the subject has used systemic or topical corticosteroids between Part B of the Screening Visit and the initiation of treatment.
6. Subject has had prolonged exposure to natural or artificial sources of ultraviolet radiation within 30 days prior to the initiation of treatment or is intending to have such

⁶ Effective forms of birth control include hormonal contraceptives [oral, injectable, transdermal or intravaginal] or intrauterine device (IUD) for two cycles (e.g., eight weeks) prior to test article application, condom and spermicidal or diaphragm and spermicidal). Other acceptable forms of birth control include: a) abstinence for subjects who are not sexually active or b) if the subject is in a monogamous relationship with a partner who is sterile (e.g., vasectomy performed at least six months prior to the subject's initiation of treatment). Subjects who become sexually active or begin to have relations with a partner who is not sterile during the trial must agree to use an effective form of birth control for the duration of the study.

exposure during the study that is thought by the investigator to likely modify the subject's disease.

7. Subject has used topical psoriatic therapy including tar, anthralin, retinoids, vitamin D analogs (e.g., Dovonex[®]) within 14 days prior to the initiation of treatment with the test article.
8. Subject has used emollients/moisturizers on areas to be treated within one day prior to the initiation of treatment with the test article.
9. Subject is currently using lithium or Plaquenil (hydroxychloroquine).
10. Subject is currently using a beta-blocking medication (e.g., propranolol) or angiotensin converting enzyme (ACE) inhibitors (e.g., lisinopril) at a dose that has not been stabilized, in the opinion of the investigator.
11. Subject has a history of sensitivity to any of the ingredients in the test article (see [Section 6.1](#)).
12. Subject is pregnant, lactating, or is planning to become pregnant during the study.
13. Subject is currently enrolled in an investigational drug or device study.
14. Subject has used an investigational drug or investigational device treatment within 30 days prior to Visit 1 (Screening).
15. Subject has been previously enrolled in this study and treated with the test article.
16. Subject has an irregular sleep schedule or works night shifts (cortisol levels exhibit physiological diurnal variation).
17. Subject has a screening Cosyntropin Stimulation Test (CST) with a post 30-minute stimulation cortisol level of $\leq 18 \mu\text{g/dL}$.
18. Subject is known to be noncompliant or is unlikely to comply with the requirements of the study protocol (e.g., due to alcoholism, drug dependency, mental incapacity) in the opinion of the investigator.

5.1.3 *Subject Withdrawal Criteria*

Procedures for handling subjects who are discontinued from the study are described in [Section 14.2](#). Subjects who are discontinued will not be replaced; however, enrollment will continue until at least 20 evaluable subjects are achieved.

6. TEST ARTICLES AND REGIMEN

6.1 Description

Halobetasol Propionate Lotion, 0.05% (HBP Lotion)

Active ingredient: Halobetasol propionate

Other ingredients:

6.2 Instructions for Use and Application

Subjects will apply a maximum of approximately 50 grams weekly of the HBP Lotion to affected areas designated by the investigator, twice daily (approximately every 12 hours) for up to two weeks. Subjects will be provided with an instruction sheet (refer to [Appendix 1](#)) which includes detailed instructions for the application of test article.

6.2.1 *Test Article Application*

A study staff member will demonstrate how to dispense the test article and instruct the subject on the proper application of the test article to the affected areas at the Baseline Visit.

All eligible subjects will apply the first dose in the clinic and be instructed to apply the assigned test article twice daily to the psoriatic plaques designated by the investigator until Day 15 or until the investigator verifies their psoriasis has cleared, whichever comes first.

Subjects should be instructed to wash their hands before and after each test article application. Instructions are as follows:

The subject will be provided with instructions on how to apply the test article (see [Appendix 1](#)). The test article should be spread uniformly to cover the psoriatic lesions designated by the investigator within the Treatment Area.

Subjects should apply the test article twice a day (approximately 12 hours apart) to all

As the subject's plaques improve or worsen the amount of test article applied will likely decrease or increase, respectively.

If the subject's disease is too extensive to be reasonably managed with the approximately 50 grams per week limitation, then the subject should not be enrolled in the study or should be discontinued from the study. Lesions not treated with test article may be managed with emollient as detailed below. If the subject's disease becomes unmanageable because of these limitations, he/she should be discontinued from the study.

At Day 8, all subjects will return to the clinic for the study staff to record percent BSA affected, record percent BSA treated, IGA, review test article compliance, and collect information on AEs and LSRs. All subjects, regardless of lesion clearance, will have blood drawn on the morning of Day 8 to assess drug concentrations in plasma (trough values). Any subject who has completely cleared their treated lesions (IGA score of 0 in Treatment Area) will discontinue dosing of test article, have a CST performed between 7 and 9AM, be assessed for any AEs and LSRs, review and document any concomitant medications, and complete EOS procedures on Day 8. If CST, AEs, LSRs, concomitant medications and EOS procedures cannot be performed on Day 8, then the subject will continue dosing of test article and return on Day 9 for morning PK, CST and all EOS procedures to be performed. Subjects who are clear at Day 8, complete CST on Day 8, and have all EOS procedures completed on Day 8 will exit the study at Day 8.

Subjects who have not cleared by Day 8 will apply their morning dose at the clinic after the Day 8 trough blood sample is drawn and continue twice-daily application of the test article until Day 15. Their percent BSA affected and percent BSA treated will be

documented at Day 8. Any AEs or LSRs (i.e., burning/stinging only) post-application will be recorded.

Subjects will apply their final dose on the evening of Day 14 and record the time of the application. The final application of test article on Day 14 should be approximately 12 hours before the final PK blood is drawn on the morning of Day 15.

At Day 15, subjects who have continued to apply test article through Day 14 will return to the clinic for the study staff to collect information on AEs and LSRs, record percent BSA affected, draw a final trough PK blood sample prior to EOS CST, and perform the EOS CST. All units of test article will be collected and weighed. If any of these subjects have adrenal suppression they will be scheduled for one or more post-treatment follow-up visits.

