Title	An Open Label Evaluation of the Adrenal Suppression Potential and Pharmacokinetic Properties of Twice Daily Halobetasol Propionate Lotion, 0.05% in Subjects 12 to 16 Years 11 Months of Age with Plaque Psoriasis Receiving Two Weeks of Treatment
Study Type	Phase 4
Test Article	Halobetasol propionate (HBP) Lotion, 0.05%
Study Objective	The objective of this study is to determine the adrenal suppression potential and the pharmacokinetic (PK) properties of HBP Lotion applied twice daily in subjects aged 12 to 16 years 11 months with stable plaque psoriasis.
Study Design	An open label, multicenter study.
Treatment Groups	All subjects will receive HBP Lotion, 0.05%.
Duration of Treatment	Up to two weeks.
Duration of Study	Participation in the study is a minimum of five weeks (at least 20 days between Screening and Baseline Visits, up to two weeks of treatment, and potential follow-up for any subjects who have evidence of hypothalamic-pituitary-adrenal [HPA] axis suppression).
Study Population	Male and female subjects aged 12 to 16 years 11 months with stable plaque psoriasis.
Total Number of Subjects	Subject enrollment will continue until at least 20 subjects with both Screening and End of Study (EOS) serum cortisol data (pre- and post-cosyntropin stimulation) have completed the study without any significant protocol violations (evaluable subjects). This may require the enrollment of approximately 25 subjects.
Number of Sites	Approximately four sites will participate in the study.
Inclusion Criteria	
To enter the study, a subject must meet the following criteria:
 
 1. Subject is male or non-pregnant female 2. Subject has provided written informed assent and was accompanied by the parent or legal guardian at the time of assent/consent signing. The parent or legal guardian has provided informed consent for the subject. 3. Subject has a clinical diagnosis of stable plaque psoriasis involving a minimum of 10% body surface area (BSA)¹ within the Treatment Area.

¹ For this evaluation 1% BSA is approximately equivalent to the area of the subject's closed hand (palm and fingers held together).

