--	---

Product Name: Halobetasol Propionate Lotion, 0.05%

Protocol: 177-0551-201

Sponsor Name: Sun Pharmaceutical Industries, Inc. Protocol Date: August 5, 2016, v3.0

Pharmacokinetic Analysis

Trough HBP concentrations in plasma on Day 8 and Day 15 will be calculated and summarized.

SCHEDE OF EVENTS

Study Day	Visit 1 Screening¹ (-Day 20 or longer)	Visit 2 Day 1 Baseline	Visit 3 Day 8 (± 1)	Optional Visit Day 9	Visit 4 EOS Day 15^{2,3} (± 2) or Early Term
Informed Consent/Assent	X				
Medical History, Demographics, Vital Signs, Height and Weight	X	Reconfirm (except height)			
Limited Physical Exam		X			
Inclusion/Exclusion Criteria	X	Reconfirm			
Urine Pregnancy Test (UPT) ⁴	X	X	X ⁵	X ⁵	X
Cortrosyn® Stimulation Test (CST)	X ⁶	Confirm eligibility ⁶	X ⁷	X ⁷	X ⁷
Percent BSA Affected with Disease	Confirm eligibility	X	X		X
Investigator's Global Assessment (IGA) Score	X	X	X	X ⁵	X ⁵
Percent BSA to be Treated with Test Article	Confirm eligibility	X	X		
Provide (or review) Instruction Sheet to Subject and Demonstrate How to Apply the Test Article		X	X		
Provide Subject Diary to Subject and Completion Instructions		X	X		
Study Treatment (approximately every 12 hours)		X	X ⁵ (withhold AM application until after trough PK blood draw)		
Concomitant Medication Assessments	X	X	X	X ⁵	X
Adverse Events Assessment	X	X	X	X ⁵	X

Study Day	Visit 1 Screening¹ (-Day 20 or longer)	Visit 2 Day 1 Baseline	Visit 3 Day 8 (± 1)	Optional Visit Day 9	Visit 4 EOS Day 15^{2,3} (± 2) or Early Term
Record Local Skin Reactions		X (pre- and post-test article application) ⁹	X (pre- and post-test article application) ⁸	X ⁵	X
Drug Accountability (with Weights)		X	X	X ⁵	X ⁹
PK Blood Draws	X		X (trough approx. 12 hours post-treatment on Day 7)	X ⁵ (trough approx. 12 hours post-treatment on Day 8)	X (trough approx. 12 hours post-treatment; Pre-CST)

1 To be performed 20 or more days prior to the Baseline visit (Day 1).

2 If results at Final Visit show evidence of adrenal suppression, testing will be performed at 4-week intervals until adrenal axis function has normalized or stabilized.

3 Final scheduled visit occurs at Day 15 ± 2.

4 All female subjects will have a UPT at Screening, Baseline and at the end of study

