 - Collect used test article after the morning application (including weights) and re-dispense test article as necessary.
 - Instruct subjects to continue twice daily application and diary activities through the evening of the day prior (Day 14) to the next clinic visit (Day 15) and remind the subject:
 - 1) to record the time of the last application of test article in the Subject Diary the evening before (Day 14) the Visit 4 (Day 15) clinic visit and,
 - 2) to NOT apply any test article on the morning of the Visit 4 (Day 15) clinic visit.
 - Query subject about the presence of any burning/stinging in the Treatment Area post-application of the test article.
 - Schedule Visit 4 (Day 15 ± 2) – The timing of this visit should occur so that the trough PK blood draw on Day 15 occurs approximately 12 hours post-treatment on Day 14.

⁷ For subjects clear at Day 8, the end of study procedures may be done the following day on Day 9 if they cannot be completed on Day 8.

⁸ If the subject has to return on Day 9 to complete end of study procedures then the subject will continue to dose on Day 8 (AM & PM dosing). The Day 9 visit must occur the day immediately after the Day 8 visit.

- Schedule the end of study visit (Day 15) for the morning so that the CST will occur at the same time (\pm one hour) as the CST performed at Visit 1 (Screening). If possible, the CST should be initiated between 7 and 9AM.

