#### 8.2.2 *Evaluable Population*

The Evaluable population will include those subjects in the Safety population who have both Screening and EOS serum cortisol data (pre- and post-cosyntropin stimulation) and meet the following criteria:

- Meets all inclusion/exclusion criteria, including normal response to cosyntropin stimulation defined as a Screening CST with a 30-minute post-stimulation cortisol level  $>18 \mu\text{g/dL}$ .
- Screening and EOS CST were conducted between 7-9 AM.
- EOS CST was conducted within  $\pm 1$  hour of the Screening CST.
- Applied at least 80% and no more than 120% of the expected number of applications and applied the final dose no more than 14 hours prior to the start of the CST test.

- Has not taken or applied any medications that may interfere with HPA axis function.
- Do not have any other significant protocol deviations.

HPA axis suppression analysis will be conducted on the Evaluable and Safety populations.

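### For a Visit 4 on Day 16 or 17, the protocol's last-dose day, two-week limit and 12-hour target cannot all be met, and two SAP summaries set no maximum time since the last dose

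*Protocol*

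**What the plan says.** **Last dose.** Protocol 6.2.1 ties the last application to a study day: "Subjects will apply their final dose on the evening of Day 14 and record the time of the application". It then adds the target interval: "The final application of test article on Day 14 should be approximately 12 hours before the final PK blood is drawn". Section 13.3 repeats the interval of about 12 hours and places the PK sample just before the CST.

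**Duration.** The synopsis gives the duration of treatment as "Up to two weeks". Section 6.2 has dosing "twice daily (approximately every 12 hours) for up to two weeks", and 6.2.2 also specifies two weeks unless psoriasis clears earlier.

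**Visit window.** Footnote 3 of the Schedule of Events reads: "Final scheduled visit occurs at Day 15 ± 2". Sections 10.3 and 10.5 carry the same window.

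**Visit 3 instruction.** Section 10.3 tells subjects to keep dosing "through the evening of the day prior (Day 14) to the next clinic visit (Day 15". It then asks sites to schedule Visit 4, window included, "so that the trough PK blood draw on Day 15 occurs approximately 12 hours post-treatment on Day 14".

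**Moving the test.** Section 13.1 sets a minimum of 8 hours off drug before the end-of-study CST and no maximum. If its conditions are not met, the test moves to the following day. It does not say whether the subject doses in between.

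**SAP.** Section 8.2.2 admits to the Evaluable population only subjects who "applied the final dose no more than 14 hours prior to the start of the CST test". Section 8.7 fixes the expected number of applications at 28 for anyone continuing to Day 15. Section 8.9.3 reports the suppression proportion for both the Evaluable and Safety populations. Section 8.9.4 summarises Day 15 trough concentrations in the PK population, whose definition (8.2.3) has no limit on the time from dose to sample.

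**The concern.** The end-of-study CST is the main endpoint, and its result depends on how recently the steroid was applied. The protocol allows the test on days for which it gives no workable dosing instruction, so two sites could handle a Day 16 or 17 visit differently, each pointing to a passage in support.

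Three things are at stake:

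- In-window subjects can be lost from the Evaluable set.
- Tests and samples taken well off drug can enter the Safety-population proportion and the trough summary without being identified.
- Some subjects may be treated for longer than the two weeks that the title and objective-related text describe, with nothing in the tables to show it.

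**Working it through.** **Inputs.** Last dose on the evening of Day 14 (Protocol 6.2.1); Visit 4 on Day 13 to Day 17 (Schedule of Events); CST between 7 and 9 AM (SAP 8.2.2); two applications a day; 28 expected applications and the 80–120% compliance rule (SAP 8.7); 14-hour limit (SAP 8.2.2); 3.5 g per application (SAP 6.3). Assumption: the evening dose is at 20:00 and the CST at 08:00. Varying these to 19:00–21:00 and 07:00–09:00 moves each interval by up to 2 hours either way.

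**The plan's own figure.** Day 1 to Day 14 is 14 days; 14 × 2 = 28 applications. This agrees with SAP 8.7.

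**Reading A: the last dose stays on the evening of Day 14.** For a visit on Day v, hours off drug = 24 × (v − 14) − 12.

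**Reading B: dosing runs to the evening before the visit.** Days dosed = v − 1; applications = 2 × (v − 1).

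| Visit 4 on | A: hours off drug (range) | B: days dosed | B: applications | B: % of 28 |
|---|---|---|---|---|
| Day 13 | visit precedes the dose | 12 | 24 | 85.7 |
| Day 14 | visit precedes the dose | 13 | 26 | 92.9 |
| Day 15 | 12 (10–14) | 14 | 28 | 100.0 |
| Day 16 | 36 (34–38) | 15 | 30 | 107.1 |
| Day 17 | 60 (58–62) | 16 | 32 | 114.3 |

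Only a Day 15 visit satisfies every passage.

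**Does A depend on the clock assumption?** No. Even a dose at midnight ending Day 14 is 24 + 7 = 31 hours before a 07:00 test on Day 16. Every late visit under A therefore misses the 12-hour target and fails the 14-hour criterion.

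**Does B show up in the compliance rule?** No. 107.1% and 114.3% both lie inside 80–120%, so the extra days pass as compliant.

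**Does B breach the weekly amount?** No. At 3.5 g per application, 32 × 3.5 = 112 g over 16 days, and 112 ÷ (16/7) = 49 g per week. The two-week course is 28 × 3.5 = 98 g, and 98 ÷ 2 = 49 g per week. The conflict is with duration and the dose count, not with the limit of about 50 g per week.

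**Room in the Evaluable set.** About 25 enrolled less 20 required leaves 5. Enrolment continues until 20 evaluable subjects are reached, but the protocol's description of an evaluable subject (18.1) does not mention the 14-hour rule.

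**Comparison with Day 8/9.** For a cleared subject whose test moves from Day 8 to Day 9, footnote 5 of the Schedule of Events and the notes to 10.3 say that dosing continues and when the last application falls. Neither Visit 4 nor the 13.1 postponement has an equivalent, so a subject who attends on Day 15 can also become a Day 16 test with no dosing instruction.

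**The case against.** The strongest reply is that Day 14 and Day 15 are nominal labels for the eve of Visit 4 and for Visit 4 itself. SAP section 5 designates Visit 4 as Day 15, Section 10.3 puts the rule before the bracketed day, and Section 13.3 refers to the dose on the previous day. This stands as the more natural reading, and it means that the either/or is not forced on sites. It does not remove the conflict: it is Reading B, which runs past two weeks and past the fixed count of 28.

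A reader might infer that the SAP discards subjects who followed the protocol in every respect. The documents do not support that. A subject tested at 36 or 60 hours has missed the protocol's own 12-hour target, and the 14-hour criterion enforces that target.

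A reader might also infer excess steroid from 112 g against 98 g. The weekly rate is unchanged, and both totals assume a full 3.5 g at every application.

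A third tempting step is to size the bias. Applying the adult lotion rate of 23.8% to 25 subjects gives about 6 suppressed, or 24%; recovery in one or two would give 20% or 16%. The documents give neither a recovery rate over 36 to 60 hours nor a number of late visits, so this is not an estimate.

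It can be said that reporting both Evaluable and Safety proportions already shows the effect of late tests. Only in part: the two populations differ on several criteria at once, so the contrast does not isolate timing.

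Finally, the content of the instruction sheet, diary and flow chart is not visible, and Administrative Amendment #1, which the SAP cites, was not available. Any of these could contain a rule.

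**Conclusion.** The point holds as an unreconciled set of passages with limited but real consequences for the main endpoint. For a Day 16 or 17 visit, one reading gives about 36 or 60 hours off drug, and the other gives 15 or 16 days and 30 or 32 applications. The late-test conclusion survives any plausible clock times, since the interval is at least 31 hours.

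The Evaluable analysis is protected from late tests, at the cost of losing in-window subjects. The Safety-population suppression proportion is not protected. Nor is the Day 15 trough summary, unless a late sample is judged a significant deviation.

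Time off drug would probably push the suppression proportion downward, because the axis may recover. The size is unknown, as it depends on the number of late visits and the speed of recovery, and the documents give neither. With about 25 treated subjects, each one moves the proportion by 1/25 = 4 percentage points. Under the other reading the concern is different: the result no longer describes two weeks of treatment for those subjects.

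This should be fixed, but it does not undermine the study. It rests on the visible text alone.

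**What to change.** **Protocol.** Reconcile 6.2.1, 6.2.2, 10.3, 13.1, 13.3, the synopsis duration and the Visit 4 window, so that one rule links the last application to the actual date of the CST, including a CST postponed by a day. That rule should agree with the SAP's 14-hour criterion and its expected-dose count. The sponsor decides which passage gives way.

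**SAP 8.9.3 and 8.9.4.** Report hours from last dose to the end-of-study CST and to the PK sample, together with actual days dosed. Section 8.7 plans days dosed only for the Evaluable and PK populations, so the Safety population needs adding. Give the Safety-population suppression proportion and the Day 15 trough summary with and without samples taken more than 14 hours after the last dose. The days-dosed figures are needed as well, because the 14-hour split does not pick out subjects who dosed beyond two weeks.

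**Cost.** Slightly tighter Visit 4 scheduling and one or two extra table rows. No new data collection is planned for: the diary records application times, and Appendix 3 (A 3.6) puts the date and time of the last application on the End of Study CRF.
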